This is a double-blind placebo-controlled study, which comprises one between-subjects factor of drink (0.4 g/kg alcohol, placebo). For the 6AFC task, there will be an additional within-subjects factor of emotion (happy, sad, angry, disgust, surprise, fear). The primary dependent variables will be accuracy and false alarms in the 6AFC task, and threshold in the 2AFC task. As 6AFC data are the primary outcome, the 6AFC task will be completed first for all participants. To investigate the subjective effects of alcohol, additional measures of intoxication and mood will be taken (see materials section) before and after drink consumption, and an additional factor of time (pre-inhalation, post-inhalation) will be included in the relevant analyses.

Study Site

School of Experimental Psychology, [name], University of Bristol, United Kingdom.

Participants and Recruitment

Male and female weekly alcohol drinkers (n = 192; 50% male) will be recruited from the staff and students at the University of Bristol, and the general population. Participants will attend one session of approximately 60 minutes. Participants will be recruited by existing email lists and poster and flyer advertisements, and by word of mouth. They will be asked to contact the researcher for further details of the study if they are interested in taking part. Those who meet the study inclusion criteria will be sent the information sheet, and asked to contact the researcher again if they would like to sign up for the study or if they require further information. Participants will be required to not drink alcohol 24 hours prior to the study session. On completion of the study, participants will be reimbursed £5.

Inclusion criteria

- Aged between 18-40 years
- Weekly alcohol drinkers (between 5-35 and 10-50 units*/week if female and male respectively)
- English as first language or equivalent level of fluency

^{*} One unit equals one 25ml single measure of spirit (ABV 40%), or a third of a pint of beer (ABV 5-6%) or half a standard (175ml) glass of red wine (ABV 12%).

Exclusion criteria

- Alcohol consumption less than 24 hours prior to the study
- Weight less than 50 kg if female or 60 kg if male
- Strong familial history of alcoholism defined as one or more immediate relative (parent, sibling) or more than one other relative (e.g., cousin, grandparent)
- History of psychiatric disorder (including drug addiction)
- Uncorrected visual impairment
- Uncorrected auditory impairment

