- Potential, in the opinion of the investigator, to be non-compliant with the study or unable to give informed consent

Sample size determination

Sample size was determined from an effect size obtained in the previous study investigating the effects of acute alcohol consumption on emotional processing. This study indicated an effect size of d = 0.41 for the comparison between alcohol (M = 4.8, SD = 4.2) and placebo (M = 3.2, SD = 3.6) on angry false alarms. Based on these data, we require a sample size of 190 in order to achieve 80% power at an alpha level of 5%. In order to maintain equal numbers of male and female participants in drink groups we will recruit 192 participants.

Randomisation

Participants will be randomly assigned to the alcohol or placebo group. Equal numbers of participants per group will be maintained and groups will be stratified by sex. In advance of the study, an experimental collaborator will prepare a numeric randomisation code using random number assignment software.

Measures

Computerised tasks: The images used in both tasks are composite (i.e., prototypical) images created from photographs of 12 young male adults photographed under controlled conditions. Each trial in both tasks begins with a centrally-displayed fixation cross. A 350×457 pixel face stimulus is then presented for 150 ms, followed by a noise mask for 250 ms in order to prevent after-image effects. Tasks are run using E-Prime 2.0 Pro software, on a standard computer with a QWERTY keyboard.

In the six alternative forced choice task (6AFC), six 15-image morph sequences have been created, one for each emotion (happy, sad, angry, disgusted, fearful, surprised). These run along a linear continuum from a neutral (i.e., emotionally ambiguous) prototype to the full emotional intensity. On each trial, participants are required to identify the emotion represented in the face as quickly and as accurately as possible, by using the mouse to click on the most appropriate descriptor from an array of descriptors displayed on-screen (fearful, angry, happy, sad, disgusted and surprised). The descriptor array appears on-screen for 10,000 ms, or until the participant responds. Each image is presented once, giving 90 trials in total.

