In the two alternative forced choice task (2AFC), one 15-image morph sequence has been created, which runs from one full emotional exemplar to another (i.e., unambiguously happy to unambiguously angry). The full exemplar images are used as endpoints to create a linear morph sequence of emotionally ambiguous images that change incrementally from happy to angry. On each trial, participants are required to identify whether the emotion in the face is happiness or anger, by pressing designated keys on the keyboard. Each image is presented three times, giving 45 trials in total.

Questionnaires: The questionnaire measures will include the Alcohol Urges Questionnaire (AUQ) (Bohn, Krahn, & Staehler, 1995), Positive and Negative Affect Schedule (PANAS) (Watson, Clark, & Tellegen, 1988), Biphasic Alcohol Effects Scale (BAES) (Martin, Earleywine, Musty, Perrine, & Swift, 1993) and Alcohol Use Disorders Identification Test (AUDIT) (Saunders, 1993).

Procedures

Participant screening and baseline assessments: On arrival, participants will be given the opportunity to read the information sheet again, and will provide written informed consent. The researcher will run through a short screening procedure to verify eligibility. Participants will be weighed and then complete questionnaire measures (AUDIT, PANAS, BAES, AUQ).

Participants will then be randomised to receive either an alcoholic or non-alcoholic drink. The alcoholic drink will be 0.4 g/kg alcohol (vodka) with one part vodka and three parts tonic water. The placebo beverage will comprise an equal volume of tonic water. All drinks will be flavoured with lime cordial and chilled prior to serving and the rim of the glass will be sprayed with an alcohol mist. Drinks will be made by a research collaborator and therefore administered double blind. This collaborator will also produce an unblinding envelope that will be passed to the researcher with the drink, which will enable the researcher to inform the participant of their drink allocation at the end of the session. Participants will be given 10 minutes to consume all of their drink and a further 10 minutes to sit quietly to allow for absorption. After drink consumption, participants will complete the two computer tasks (see below) and then questionnaire-based measures of mood (PANAS), intoxication (BAES), and alcohol urges (AUQ). Finally, participants will be asked to give another breath alcohol reading before being debriefed and reimbursed.

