Table 1. Timings of procedures of testing session

Time (minutes post arrival)	Task
0	Informed consent and screening
15	Questionnaire measures (4)
20	Drink administration
40	Task 1 – Emotional 6AFC
50	Task 2 – Emotional 2AFC
55	Questionnaire measures (3)
60	Debrief and depart

Statistical Plan

Analysis of the questionnaire scores will be conducted using mixed model ANOVAs with alcohol consumption (alcohol vs. placebo) as a between-subjects factors and time as a within subjects factor (before alcohol consumption, after alcohol consumption). Emotional task data from both tasks will also be analysed using ANOVAs with alcohol consumption as a between-subjects factor. The 6AFC task will have an additional within-subjects factor of emotion.

Ethical Considerations and Informed Consent

Ethics approval has been obtained from the Faculty of Science Research Ethics Committee at the University of Bristol. The study will be conducted according to the revised Declaration of Helsinki (2013) and good clinical practice guidelines. The investigator will explain the nature, purpose and risks of the study to the participant. The participant will receive the information sheet in advance of the study session. There will be no time restriction on how long participants take to respond, with the exception that participants who respond after all study places have been filled will not be offered a place on the study. Therefore, participants will be given sufficient time to read the information and consider any implications, and to raise any questions with the investigators prior to making a decision to participate. On arrival at the study session participants will be given the opportunity to read the information sheet again and ask the investigator any questions. Written consent will then be obtained. Participants will be informed that they are free to withdraw at any time.

Data Management

All aspects of the Data Protection Act will be adhered to. Consent forms will be retained by the School of Experimental Psychology. In the event that a participant revokes authorisation to collect or use personal health information, the investigator retains the ability to use all information collected prior to the revocation of participant authorisation.

Anonymised study data

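### PANAS, BAES and AUQ are analysed by a drink × time ANOVA, although adjusting the post-drink score for its pre-randomisation baseline would be at least as precise at no cost

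*Protocol*

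**What the plan says.** The Statistical Plan fixes the model for the questionnaires: "Analysis of the questionnaire scores will be conducted using mixed model ANOVAs with alcohol consumption (alcohol vs. placebo) as a between-subjects factors". The model's second factor, within participants, is time, with one level ahead of the drink and one following it. The Study Design section describes the same structure: "an additional factor of time (pre-inhalation, post-inhalation) will be included in the relevant analyses". Its level labels refer to inhalation; since the intervention is a drink, I read them as pre-drink and post-drink.

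Under Procedures, the first administration is at baseline: "Participants will be weighed and then complete questionnaire measures (AUDIT, PANAS, BAES, AUQ". Randomisation to drink comes next. After both computer tasks the participant completes "questionnaire-based measures of mood (PANAS), intoxication (BAES), and alcohol urges (AUQ". Table 1 puts the two administrations at 15 and 55 minutes, with the drink given at 20 minutes. AUDIT is taken only at baseline, so the before/after model concerns PANAS, BAES and AUQ.

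The purpose of these scales is stated in Study Design: "To investigate the subjective effects of alcohol, additional measures of intoxication and mood will be taken". They are not among the primary dependent variables, which come from the two face tasks. The protocol does not say which term of the ANOVA tests the drink effect, and it does not adjust the post-drink score for the pre-drink score.

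**The concern.** A score taken before randomisation cannot be affected by the drink. Entering it as one of two outcome levels leaves two terms that involve drink, and each has a drawback.

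- **Drink × time interaction.** With two time points this is the between-group comparison of post minus pre. It subtracts the whole baseline score even when the baseline predicts only part of the post-drink score, so it can carry unnecessary noise. It also over-corrects for a chance baseline difference whenever the slope of post on pre is below 1.
- **Drink main effect.** This averages an unaffected score with an affected one, and so dilutes the difference.

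What is at stake is how clearly the trial can show whether this dose changed mood, felt intoxication and urge to drink. The Safety section expects some effects but not high levels of intoxication, so the subjective differences may be modest and precision is worth having.

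**Working it through.** **1. The protocol's own figure.** Sample size determination gives means 4.8 and 3.2 and SDs 4.2 and 3.6 for angry false alarms. The pooled SD is √((4.2² + 3.6²)/2) = 3.91, so d = 1.6/3.91 = 0.41. At two-sided 5% and 80% power, the normal approximation gives 94 per group (188) and the t-test gives 95 per group (190). The stated 190 is reproduced. It concerns the 6AFC task, so it neither supports nor weakens the point about the questionnaires.

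**2. Inputs for the comparison.**
- 192 participants in two equal groups, so 96 per group (Sample size determination; Randomisation).
- Pre-post correlation r: not given; shown for 0.3, 0.5 and 0.7.
- Equal pre and post SDs, set to 1: assumed, and relaxed in step 4.
- Post-drink difference d = 0.41 SD: borrowed from the 6AFC outcome as an illustration. The protocol gives no effect size for any questionnaire.

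**3. What each analysis estimates, with its per-person variance.**
- Drink main effect: (0 + d)/2 = d/2, that is 0.205 for d = 0.41.
- Drink × time interaction (change score): d, with variance 2(1 − r).
- Post score adjusted for pre score: d, with variance 1 − r².
- Ratio of interaction to adjusted variance: 2(1 − r)/(1 − r²) = 2/(1 + r).

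**4. Without equal SDs.** Let the pre SD be s and the post SD 1, so that the slope of post on pre is b = r/s. The change-score variance is 1 + s² − 2rs and the adjusted variance is 1 − r². Their difference is s² − 2rs + r² = (s − r)² = s²(1 − b)². This is never negative, and it is zero only when b = 1. For example, with r = 0.5 and s = 0.5 the change score gives 1 + 0.25 − 0.5 = 0.75 and the adjusted analysis gives 1 − 0.25 = 0.75, so nothing is lost. Estimating the slope costs one degree of freedom, which is negligible with 192 participants.

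**5. Results with equal SDs, d = 0.41, 96 per group, two-sided 5%.**

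| r | Variance, interaction | Variance, adjusted | Ratio | Power, interaction | Power, adjusted |
|---|---|---|---|---|---|
| 0.3 | 1.40 | 0.91 | 1.54 | 67% | 84–85% |
| 0.5 | 1.00 | 0.75 | 1.33 | 81% | 90–91% |
| 0.7 | 0.60 | 0.51 | 1.18 | 95–96% | 98% |

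Where a range is shown, the lower figure uses the noncentral t and the upper the normal approximation. At r = 0.8 the variance ratio falls to 1.11. Below r = 0.5 the change score has variance above 1, and so is less precise than the post-drink score used alone.

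**6. Simulation check** (4,000 runs at each r, true difference 0.41). The mean estimate was 0.41 for the interaction and for the adjusted analysis, and 0.20–0.21 for the main effect. Simulated power for interaction and adjusted analysis was 67% and 84%, 81% and 91%, and 96% and 98%.

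**7. Chance imbalance.** With equal SDs, a baseline difference of D between groups shifts the change-score estimate by −(1 − r)D. Baseline adjustment removes this shift.

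**The case against.** The strongest reply is that nothing planned here is invalid. Under randomisation the drink × time test is unbiased and has its nominal error rate, and it is a conventional analysis for a before/after design. That stands: for this term the issue is efficiency, not bias.

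A reader might infer that the plan will report a halved alcohol effect. The document does not support that. It never names the drink main effect as the test, and a before/after factor points naturally to the interaction. What can be said is that the term is left unnamed and that one of the two candidates would mislead.

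A reader might also infer that the change score loses precision whenever the pre-post correlation is below 1. That needs equal pre and post SDs, which the protocol does not give. They are not obvious for an alcohol-effects scale completed once before and once after a drink. If the slope happens to be 1, nothing is lost.

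Three further points stand. The 0.41 SD is not a questionnaire effect. The two administrations are about 40 minutes apart in one session, so r may be high and the loss small. The scales are also not the only evidence on alcohol exposure, because a breath alcohol reading is taken at the end of the session. That reading shows exposure rather than subjective effect, so it does not replace the scales.

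**Conclusion.** The point holds as an available improvement to a valid analysis. The protocol fixes a model that treats a true baseline as an outcome level; adjusting for that baseline is, in large samples, never less precise, and it is more precise unless the slope of post on pre is 1. With equal SDs the interaction's variance is 18% to 54% larger for r from 0.7 down to 0.3. In the illustration this costs about 2 to 17 percentage points of power. These sizes depend on the assumed r, the equal-SD assumption and a borrowed effect size; the ordering of the two methods does not. The unnamed test term adds a smaller risk of misreading.

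The documents do not support calling this a bias or a threat to the trial's main conclusions. The affected scales are additional measures, and H1, H2 and the sample size do not depend on them.

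**What to change.** In the Statistical Plan, replace the drink × time ANOVA for PANAS, BAES and AUQ with a linear model for each post-drink score. The model contains drink group, the same scale's pre-drink score and sex (the stratification factor). Report the adjusted drink difference with its 95% CI.

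If the ANOVA is kept, name drink × time as the test of the drink effect, and state that the drink main effect will not be interpreted. In either case, correct the labels of the time factor in Study Design to pre-drink and post-drink.

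The cost is a change of wording. All the data needed are already collected, and participant numbers, procedures and timing stay as they are.

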School of Experimental Psychology [name] United Kingdom

[name] t. [name] f. [contact] www.bristol.ac.uk

STUDY PROTOCOL

Effects of alcohol consumption on emotion recognition

[name], [name], [name], [name]

Background Information

Alcohol is often consumed in social settings whilst in the company of others. Recent research has begun to examine the effects of acute alcohol consumption on the processing of socially relevant information such as facial expressions, as it may play a role in the changes in social interaction associated with alcohol consumption (e.g., increased aggression) (Attwood & Munafo, 2014; Hoaken, Giancola, & Pihl, 1998; White, 1997; Yudko, Blanchard, Henrie, & Blanchard, 1997). Recent research has indicated that acute alcohol consumption decreases sensitivity to recognising sad facial expressions (Craig, Attwood, Benton, Penton-Voak, & Munafo, 2009) and increases the likelihood of perceiving anger in ambiguous facial morphs (Attwood, Ataya, Benton, Penton-Voak, & Munafo, 2009). To date this research is limited, with studies only examining the effects of alcohol on a small number of emotions.

We recently explored the effect of acute alcohol consumption (0.4 g/kg) on emotional face processing using a task that presents all six primary emotional expressions (i.e., anger, sadness, happiness, surprise, disgust and fear). We found no difference between alcohol and placebo in accuracy of emotional identification, but there were greater false alarms for anger after alcohol compared to placebo (i.e., individuals were more likely to erroneously label a non-angry face as angry). In addition, alcohol consumption was associated with fewer false alarms for happiness compared to placebo. The current study will attempt to replicate these findings using the same six alternative forced-choice task (6AFC). In addition, this study will include a two alternative forced choice task (2AFC) presenting angry and happy facial morphs, to investigate whether there is a bias towards the identification of anger after acute alcohol consumption.

Study Objective and Hypotheses

To replicate preliminary work on the effects of acute alcohol consumption on emotional face processing.

H1: Acute alcohol consumption will result in more false alarms for anger compared to placebo.

H2: Acute alcohol consumption will result in fewer false alarms for happiness compared to placebo.

Study Design

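### The 80% power belongs to a two-group comparison of anger false alarms (H1), but the Statistical Plan names only a drink × emotion ANOVA for the 6AFC, and neither of its drink tests is a test of H1 or H2

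*Protocol*

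**What the plan says.** Study Objective and Hypotheses gives two directional hypotheses, each about one emotion: "H1: Acute alcohol consumption will result in more false alarms for anger compared to placebo" and "H2: Acute alcohol consumption will result in fewer false alarms for happiness compared to placebo".

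Sample size determination takes one contrast from the earlier study, an "effect size of d = 0.41 for the comparison between alcohol (M = 4.8, SD = 4.2) and placebo (M = 3.2, SD = 3.6) on angry false alarms", and concludes that "we require a sample size of 190 in order to achieve 80% power at an alpha level of 5" per cent. The recruitment target is then rounded up to 192, with equal groups stratified by sex (Randomisation).

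The Statistical Plan assigns both emotion tasks to ANOVAs with drink as the between-subjects factor and adds: "The 6AFC task will have an additional within-subjects factor of emotion". Study Design lists the six levels of that factor and calls the 6AFC data the primary outcome. No contrast, simple effect or follow-up for anger or happiness is named anywhere in the protocol.

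**The concern.** A 2 × 6 mixed ANOVA gives two tests that involve drink. The main effect compares the groups on the average over six emotions. The interaction, on 5 degrees of freedom, asks whether the drink effect differs among emotions. H1 and H2 are each a group difference on one named emotion, in a named direction. Neither ANOVA test is that comparison, so the stated power is attached to a test that the stated analysis does not contain.

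At stake is how the primary question is answered. A significant interaction could come from sadness or fear and would not by itself confirm H1. With no comparison named, any of six per-emotion comparisons could be chosen after the data are seen, in a study whose purpose is to replicate two specific findings. The 80% figure could also be read as the power of the ANOVA, for which the protocol gives no basis.

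**Working it through.** **Inputs from the protocol.** Anger false alarms 4.8 (SD 4.2) versus 3.2 (SD 3.6); d = 0.41; 80% power; alpha 5%, sidedness not stated; 192 participants, so 96 per group; six emotions.

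**Assumptions, not in the protocol.** A common SD for all six scores, a common correlation ρ between them, and the drink effects on emotions other than anger.

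**1. Reproducing the sample size.** Pooled SD = √((4.2² + 3.6²)/2) = √15.3 = 3.91, and d = 1.6/3.91 = 0.409. A two-sided 5% two-sample t-test with d = 0.41 needs 95 per group, which is the stated 190; a one-sided test would need about 150. Power is 80.3% at 95 per group and 80.7% at 96. The stated N is therefore correct for a direct, two-sided comparison of anger false alarms.

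**2. Drink main effect.** With n = 96 per group and δ̄ the mean drink effect over the six emotions,

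λ = (n/2) × 6 × δ̄² / (15.3 × (1 + 5ρ)), referred to F(1, 190).

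- Only anger moves: δ̄ = 1.6/6 = 0.267. At ρ = 0, λ = 48 × 6 × 0.0711/15.3 = 1.34 and power is 21%. At ρ = 0.6, λ = 0.33 and power is 9%.
- Anger +1.6, happiness −0.8: power 9% at ρ = 0, 6% at ρ = 0.6.
- Any pattern summing to zero: δ̄ = 0, so 5%, the test's own error rate.

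A near-zero sum is a reasonable expectation. In a forced-choice task, if every trial is answered, total false alarms equal total errors, and Background Information reports no accuracy difference in the earlier study.

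**3. Drink × emotion interaction.**

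λ = (n/2) × Σ(δⱼ − δ̄)² / (15.3 × (1 − ρ)), referred to F(5, 950).

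| Drink effects | Σ(δⱼ − δ̄)² | λ at ρ = 0 | Power, ρ = 0 | ρ = 0.3 | ρ = 0.5 |
|---|---|---|---|---|---|
| Anger +1.6 only | 2.133 | 6.69 | 48% | 65% | 82% |
| Anger +1.6, happiness −0.8 | 3.093 | 9.70 | 66% | 83% | 94% |
| Anger +1.6, other five −0.32 each | 3.072 | 9.64 | 66% | 83% | 94% |
| Anger +1.6, happiness −1.6 | 5.120 | 16.06 | 89% | 98% | >99% |

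Power reaches 80% with anger alone at ρ of about 0.48, in the second and third rows at ρ of about 0.25, and at ρ = 0 once happiness falls by about 1.25. At ρ = −0.1 the anger-only figure is 44%.

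**4. Direct contrasts.** At 96 per group, H1 has 80.7% power at two-sided 5%. Splitting alpha at 2.5% each for H1 and H2 gives 71.9%, and 115 per group (230) would be needed to restore 80%. The protocol gives no effect size for H2; at 5% its power is 28%, 54% or 81% for an assumed d of 0.20, 0.30 or 0.41.

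**The case against.** A reader might infer that the planned ANOVA is underpowered in general. The documents do not support that for the interaction. Its power depends on the happiness effect, the correlation between emotions and the SDs of the other five scores, and the protocol gives none of these. If H1 and H2 hold at equal size, which fits the protocol's own predictions, interaction power at equal SDs is 85% or more for any ρ of −0.1 or above. Smaller SDs for the other emotions would raise it and larger ones would lower it. Nor is the main effect without power in every case: the 5% figure needs an exact zero sum, and a negative correlation with only anger moving would raise it above the 21% shown.

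A reader might also infer that a real anger effect will be missed because the omnibus test must be significant first. The protocol states no such gate and rules out no follow-up comparison. Its hypotheses already identify emotion, direction and groups, and the sample size section is explicit that it concerns anger. Follow-up contrasts and sphericity correction are commonly left to an analysis plan, and one may exist unseen.

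These points limit the concern without removing it. The protocol has its own Statistical Plan, which fixes a model for the primary task, and that model's drink tests are not the comparison the trial was sized for. This is a mismatch between two stated passages, and it remains however powerful the interaction test turns out to be.

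**Conclusion.** The point holds as a mismatch, and its weight is moderate. N = 190 reproduces and is right for a two-sided comparison of anger false alarms; the Statistical Plan does not name that comparison. The main effect is a poor vehicle for opposed hypotheses, with power of about 5–21% at equal SDs and ρ of 0 or more. The interaction cannot identify the emotion or the direction. Its power is unestablished rather than shown to be inadequate: 48%, 66% or 89% at ρ = 0 as the fall in happiness false alarms goes from none to half to all of 1.6, and higher as ρ rises. These power figures rest on a common SD of 3.91 and a common correlation, which are assumptions. The mismatch itself rests on the protocol text alone.

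**What to change.** In the Statistical Plan, state that H1 is tested by a two-sided 5% between-group comparison of anger false alarms and H2 by the same comparison for happiness false alarms, both run and reported whatever the omnibus result. Keep the 2 × 6 ANOVA as supportive, with a sphericity correction.

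Fix the alpha handling before data are seen. One workable choice is H1 as the single primary test at 5%, with H2 next in order and confirmatory only if H1 is significant; this keeps about 80.7% power for H1 at N = 192. If an even split is preferred, the protocol should acknowledge 71.9% for H1 or move to 230 participants. State that the 80% applies to the H1 comparison only.

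With the ordered approach the cost is one paragraph of wording, with no extra participants or data.
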